### 2) Objectives and Hypothesis(es)

The project goal is to investigate the efficacy of proning COVID-19 hypoxemic patients who are hospitalized at Baylor St. Luke's in an acute care, telemetry-monitored unit. The researchers will be using a systematic approach to educate patients and staff about patient self-proning, implementing self-proning every 2 hours, and monitoring escalation of oxygen levels, as well as length of the study period.

**Objectives:** This study is intended to explore the effects of proning on non-ventilated COVID-19 hypoxemic patients hospitalized in a telemetry-monitored, acute care unit. In addition, the hope is to delay intubation and/or escalation of respiratory interventions, while contributing to the growing body of knowledge related to COVID-19 treatment and care.

**Hypotheses:** The researchers expect to see an improvement in oxygen saturation levels as evidenced by no escalation of respiratory care (i.e. higher levels of oxygen needed, transfer to higher level of care), resulting in shorter lengths of stay for the intervention population.

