## **7) Study Endpoints**

Primary endpoint of this study is a shorter length of stay for the intervention group. Secondary endpoints include decreased need for oxygen supplementation as evidenced by higher oxygen saturation levels, decreased need to be admitted to the intensive care unit, and decreased reports of pressure injuries (as identified by BSLMC protocol).

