## **8) Procedures Involved**

**Study Design:** This will be a prospective randomized cohort study in which data will be collected for over 14 days or until discharged or transferred to a lower level of care from the telemetry-monitored, acute care unit. Data collected on study participants will include the need for escalating respiratory care as well as length of stay in the acute care unit. Comparative analysis will be conducted with retrospective data collected from hospitalized patients (the control group) with a diagnosis of COVID-19 on a non-ICU acute care, telemetry-monitored unit that meets the hypoxemia criteria, but that will not receive the proning intervention. The data from the control group will be collected by a retrospective chart analysis after 14 days past their discharge date.

On a confirmed COVID-19 non-ICU acute care, telemetry-monitored unit, there will be two sets of patients: patients that will receive the intervention of proning plus standard of care, and patients that receive standard of care, but not the proning intervention. Confirmed COVID-19 positive patients are randomly assigned by bed control to a room upon admission to the unit. Patients will be randomized upon admission to the acute care, telemetry-monitored unit, and selected based

on inclusion criteria. The patients that will be prone will be identified by a door slot "slider" that is purple. Timing devices will be purchased and placed at the nurses' station, and checklists to indicate proning times will be placed inside the room with a patient identification sticker. The researchers will be following the proning protocol for acute care patients provided by CommonSpirit Health (CSH).

Patients will consent to participation (using an approved consent document from the CSH IRB), and an order for the proning protocol will be entered in the EMR by the physician. The patient will be educated about self-proning, and instructed to self-prone every 2 hours. The nursing staff will document patient position on the checklists every 2 hours.

1. Upon initiation of the initial proning, the patient will be monitored by the RN for adverse effects for 15 minutes (such as inability to tolerate position or signs of respiratory distress).

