2. If the patient tolerates the proning well, the procedure can continue and the RN will set the timer for 2 hours, enter the patient's oxygen saturation into the EMR, and document the position (prone or supine) on the checklist. O2 saturation will be documented at least every 4 hours per unit protocol.
3. The 2 hour timer will be reset each set of 2 hours by the nursing staff, and the intervention will continue until the end of the study period or until the patient is discharged or transferred from that unit.
4. The checklists will be placed in a binder at the nurses' station at the end of each shift and collected daily by a member of the research team.
5. This intervention for each "proned" patient will continue until either of the following occur: either the patient is discharged or transferred to a lower level of care from the acute care floor, or 14 days have passed.
6. A retrospective chart review will be completed by the research team to ascertain length of stay on the acute care, telemetry monitored unit, as well as the need for escalation of respiratory care. Escalation is defined by a need for oxygen requirements above 6 liters of oxygen on the nasal cannula.

*If the patient is assigned to the control group, that patient will receive the standard of care treatment designated by BSLMC policy per their condition on the COVID-19, acute care, telemetry-monitored unit.*

**Data Analysis:** Retrospective data analysis will be conducted by the research team with data collected from the electronic medical record as well as the checklists (oxygen saturation, demographics, proning protocol) for both the interventional and control group. See attached documents for consent/proning protocol documents.

This study will be a prospective cohort study in which data will be collected on subjects for the designated time period. Data will be collected from the electronic medical record as well as the checklists. Data collection will include basic patient demographics, specifically age and gender, height, weight and ethnicity. Clinical data to be collected include O2 saturation, respiratory support methods, proning duration/compliance, presence of hospital acquired pressure injuries,

and need to escalate care to ICU, including initiation of mechanical ventilation. The same data will be collected for the control group - except for proning duration/compliance as they will not receive this intervention.

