## **9) Data and Specimen Banking**

The data obtained from this study will be basic patient demographics, specifically age and gender, height, weight and ethnicity. The patient medical record number, name, and date of admission/discharge are included as PHI necessary to complete this study. Clinical data to be collected include O2 saturation, respiratory support methods, proning duration/compliance, presence of hospital acquired pressure injuries, and need to escalate care to ICU, including initiation of mechanical ventilation. The REDCap project IDs are 2817 and 3682 for reference.

Upon consent to the study, the patient's medical record number will be recorded as the principal identifier, and the above demographic data will be collected from the electronic medical record. This information will be coded to a personal ID generated by the researchers' REDCap software by the principal investigator or members of the research team. The clinical data obtained during and after the intervention will be recorded from the electronic medical record and also linked to the personal ID in the REDCap software.

The list linking the medical record number to the personal ID will only be handled by members of the research team and will be destroyed electronically upon completion of data collection - approximately 8 months after the initial start of the study. This is to allow for easy access of associated data as the researchers update the ID profiles. All of the members of the research team have completed CITI training, as well as financial conflict of interest records.

The researchers do not anticipate any incidental findings that would impact the outcome of this study or the care of the patient. If the patient started the study and then wished to have their data removed, the patient would communicate that to the nurse assigned, who would then call the principal investigator (number provided to the unit). The investigator would then delete the profile from REDCap and remove the medical record number from the study records.

Data collection will proceed as follows:

1. Every calendar day after the patient has been consented and the intervention is occurring, the nurse assigned to the patient will chart O2 saturation, any presence of hospital acquired pressure injuries, and need to escalate care. This data will be recorded in the electronic medical record, and members of the research team will daily update the REDCap profile with that data.

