## **10) Data Analysis Plan**

Retrospective data analysis will be conducted by the research team with data collected from the electronic medical record as well as the checklists (oxygen saturation, demographics, proning protocol) for both the interventional and control group. See attached documents for consent/proning protocol documents.

This study will be a randomized controlled trial. The primary outcome will be time (days) until discharge from the acute care unit to home or lower level of care (e.g., long-term care), and the primary hypothesis test will compare time-to-discharge between "prone" and "not prone" treatment arms.

A sample size of 48 patients per group (N=96) will provide 80% power to detect a 50% decline in time-to-discharge using a log-rank test.

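### Sections 7 and 8 word and collect the primary outcome as length of stay (on the unit), while Section 10 defines it as time to discharge home or to lower care; the two part for patients who go to ICU or die

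*Protocol*

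**What the plan says.** Section 7: "Primary endpoint of this study is a shorter length of stay for the intervention group". It names no end event and does not say whether the stay is on the unit or in hospital.

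Section 8, study design: "Data collected on study participants will include the need for escalating respiratory care as well as length of stay in the acute care unit". Step 6 repeats this as the item to extract from the chart: "A retrospective chart review will be completed by the research team to ascertain length of stay on the acute care, telemetry monitored unit". Neither sentence depends on where the patient goes next.

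Section 10: "The primary outcome will be time (days) until discharge from the acute care unit to home or lower level of care". The primary hypothesis test compares time-to-discharge between the arms, and the sample size rests on it: "A sample size of 48 patients per group (N=96) will provide 80% power to detect a 50% decline in time-to-discharge using a log-rank test".

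On ICU transfer, Section 2 expects "no escalation of respiratory care (i.e. higher levels of oxygen needed, transfer to higher level of care), resulting in shorter lengths of stay", and Section 7 lists "decreased need to be admitted to the intensive care unit" as a secondary endpoint. Section 12 names intubation among possible harms.

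On data, Section 9 step 1 has daily charting while the intervention is under way: "the nurse assigned to the patient will chart O2 saturation, any presence of hospital acquired pressure injuries, and need to escalate care". Section 8 collects escalation to ICU in controls too, and Section 9 lists admission and discharge dates. Date of ICU transfer is not listed, and death is on no data list. The only censoring rule, in Section 11, concerns withdrawal.

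**The concern.** The primary outcome is described in two ways that classify some patients in opposite directions. A patient moved to ICU on day 2 has a two-day unit stay, which under a shorter-is-better endpoint is a good result. Under Section 10 that patient has not been discharged.

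This would matter little if treatment did not affect ICU transfer. The protocol expects that it does. If proning prevents ICU transfers, the patients it keeps on the unit have longer unit stays, and the comparison is pulled against proning. If proning leads to more transfers, the early exits shorten proned stays and the comparison is pulled in its favour. The data-collection wording points to the quantity with this problem.

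**Working it through.** **1. The wordings side by side**

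| Patient leaves the unit by | Unit stay (Section 8) | Section 10 outcome |
|---|---|---|
| Discharge home or to lower care | stay ends | event |
| Transfer to ICU | stay ends, counted short | not an event |
| Death | stay ends, counted short | not an event |

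Only the last two rows differ.

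**2. The plan's own figure.** A 50% decline is taken as hazard ratio 2 (exponential times). Alpha is not stated; 5% two-sided is assumed.
- Schoenfeld: 4(1.96 + 0.84)²/(ln 2)² gives 66 events. Freedman: (1.96 + 0.84)² × (3/1)² gives 71.
- 66/96 = 69% and 71/96 = 74% of patients with an event.
- With a 7-day control median and a 14-day cap, the share not discharged is 0.5² = 0.25 in controls and 0.5⁴ = 0.0625 with proning. Events are 48 × 0.75 + 48 × 0.9375 = 81, and power is about 88%.

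The stated 80% is therefore attainable. It can be neither confirmed nor refuted, because alpha and the event share are not given.

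**3. Inputs for the illustration.** From the protocol: 48 per arm, log-rank, 50% decline, 14 days. Assumed: control discharge hazard d = ln 2/7 = 0.099 per day, constant hazards, whole-day times, two-sided 5%, and the ICU/death shares. The ICU/death hazard h solves

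h/(d + h) × [1 − exp(−14(d + h))] = stated 14-day share.

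For a control share of 20%, h = 0.0310: 0.0310/0.1300 × (1 − e^−1.82) = 0.20.

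**4. Why unit stay dilutes the effect.** Unit exit adds both hazards. For 20% falling to 10% with the discharge hazard doubled, the proned ICU/death hazard solves to 0.0232. The hazard ratio for any exit is (0.198 + 0.0232)/(0.099 + 0.0310) = 1.70, not 2.

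**5. Simulated power, expected direction, hazard ratio 2** (20,000 trials per setting; 87.5% with no ICU or death)

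| ICU/death, control to prone | Unit stay | Section 10 event, censored at ICU/death | Section 10 event, kept at risk to day 14 |
|---|---|---|---|
| 28% to 14% | 57% | 82% | 74–80% |
| 20% to 10% | 68% | 83% | 78–81% |
| 10% to 5% | 80% | 86% | 83–84% |

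In the last column the lower figure has half of the ICU/death patients discharged later (mean 4 further days, assumed); the higher figure has none.

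At hazard ratio 1.5, unit stay gives 13%, 21% and 32%, against 38%, 40% and 41% with censoring.

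**6. Opposite direction: equal discharge hazards, ICU/death doubled by proning.** Share of trials in which unit stay shows a significant benefit (nominal 2.5%):

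| Control to prone | False benefit |
|---|---|
| 20% to 40% | 28% |
| 14% to 28% | 15% |
| 10% to 20% | 9% |
| 5% to 10% | 5% |

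Control medians of 5 or 10 days move these by little more than one point. The Section 10 event censored at ICU/death gives 1.9% to 2.5% in the same settings.

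**The case against.** The strongest reply is that the protocol is more consistent than it first looks. Only Sections 7 and 10 use the word primary. Section 7 is shorthand that Section 10 makes specific, and step 6 of Section 8 is a chart-extraction line. The collection window at the head of Section 8, its step 5 and the benefit listed in Section 13 all use an end event close to Section 10's. This stands: Section 10 most likely governs.

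A reader might infer that the trial will analyse any exit from the unit, so that its primary result is biased. The documents do not support that. No passage plans such a test, and the unit-stay figures apply only if the collected quantity were analysed. A reader might also treat the absence of a rule for ICU transfer and death as an error in itself. That detail may properly sit in an analysis plan that is not shown, and the choice between censoring and keeping patients at risk is partly a choice of estimand.

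The data gap is also modest: transfer and death dates could be expected in the electronic record, though the protocol does not list them.

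What remains is that the sections disagree about the primary outcome and nothing says which prevails. An analysis plan could add a handling rule, but the protocol's wording would still conflict.

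**Conclusion.** The inconsistency is real and should be fixed. It is one of wording and data collection, confined to patients who go to ICU or die, and Section 10 probably prevails. If unit stay were analysed, the illustration puts the power loss against the censored Section 10 event at about 25, 15 and 6 points for the three expected-direction settings, and the false-benefit rate at 5% to 28%. These sizes rest on assumed ICU/death shares, a 7-day median, constant hazards and a two-sided 5% level; the documents supply none of these. Patients needing ICU-level respiratory care are excluded at entry, and if later ICU transfer and death are rare the effect is small. Confidence is high for the mismatch, not for any single percentage.

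**What to change.** Use the Section 10 definition in Sections 7 and 8 as the single primary outcome, over the same 14 days in both arms, and state that ICU transfer or death is never a completed stay. Record the date of ICU transfer and the date of death in both arms from the chart review.

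Suggested handling: keep these patients as not discharged unless they are actually discharged alive to home or lower care by day 14, with the log-rank censored at ICU transfer or death as supportive. The choice between the two may be fixed in the SAP. State the Section 10 power for the handling chosen.

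The wording and two dates cost little. The at-risk rule costs power against censoring, at hazard ratio 2:

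| Control ICU/death share | Proning changes the discharge hazard only: censored, then at risk | Same ICU/death share in both arms: censored, then at risk |
|---|---|---|
| 5% | 87%, 84–85% | 86%, 78–82% |
| 10% | 85%, 79–81% | 84%, 67–76% |
| 20% | 82%, 71–73% | 80%, 47–62% |

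Here the lower figure has none of these patients discharged later, the higher has half. In the first setting the at-risk rule does no better than unit stay (about 84–85%, 82% and 74%). The second setting is not one where proning acts on discharge alone. With the discharge hazard doubled and h unchanged, a 20% control share falls to 0.0310/0.2290 × (1 − e^−3.21) = 13% with proning. Equal shares therefore require a 1.6- to 1.7-fold higher ICU/death hazard with proning.

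Separately, steps 3 and 5 of Section 8 differ on which transfers end the intervention, and those passages must be reconciled.

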## **9) Data and Specimen Banking**

The data obtained from this study will be basic patient demographics, specifically age and gender, height, weight and ethnicity. The patient medical record number, name, and date of admission/discharge are included as PHI necessary to complete this study. Clinical data to be collected include O2 saturation, respiratory support methods, proning duration/compliance, presence of hospital acquired pressure injuries, and need to escalate care to ICU, including initiation of mechanical ventilation. The REDCap project IDs are 2817 and 3682 for reference.

Upon consent to the study, the patient's medical record number will be recorded as the principal identifier, and the above demographic data will be collected from the electronic medical record. This information will be coded to a personal ID generated by the researchers' REDCap software by the principal investigator or members of the research team. The clinical data obtained during and after the intervention will be recorded from the electronic medical record and also linked to the personal ID in the REDCap software.

The list linking the medical record number to the personal ID will only be handled by members of the research team and will be destroyed electronically upon completion of data collection - approximately 8 months after the initial start of the study. This is to allow for easy access of associated data as the researchers update the ID profiles. All of the members of the research team have completed CITI training, as well as financial conflict of interest records.

The researchers do not anticipate any incidental findings that would impact the outcome of this study or the care of the patient. If the patient started the study and then wished to have their data removed, the patient would communicate that to the nurse assigned, who would then call the principal investigator (number provided to the unit). The investigator would then delete the profile from REDCap and remove the medical record number from the study records.

Data collection will proceed as follows:

1. Every calendar day after the patient has been consented and the intervention is occurring, the nurse assigned to the patient will chart O2 saturation, any presence of hospital acquired pressure injuries, and need to escalate care. This data will be recorded in the electronic medical record, and members of the research team will daily update the REDCap profile with that data.
2. The nurse assigned to the patient will also chart the position of the patient every 2 hours via a paper document (also attached). These paper documents will be placed in a binder at the nurse's station at the end of each shift and collected by the research team daily. The research team will document for each profile the patient's compliance with proning.

The risk of loss of confidentiality will be minimized by taking the following steps: (1) Data collected from study participants will be maintained in locked file cabinets or in password protected CHI servers managed and maintained by CHI Information Technology. (2) Subject names and other identifiers will be removed from study data and will be replaced by unique study numbers. (3) The documents connecting the subjects to their study

numbers will be kept separately from subject data and in locked file cabinets, in password protected CHI servers managed and maintained by CHI IT. (4) Study personnel will be the only individuals with filing cabinet keys and computer passwords. Study personnel will only access this data while at work.

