## **12) Risks to Subjects**

The researchers foresee minimal risks in this study to the participant. Possible risks include:

- Inability to maintain the prone position, possibly resulting in O2 desaturation and other negative respiratory effects, such as intubation
- Skin breakdown
- Patient discomfort in turning every 2 hours/patient inconvenience for documentation, especially overnight

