### ***Waiver or Alteration of the Consent Process***

For our patients assigned to the control group, a waiver of consent will be requested.

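### Pressure injuries are actively prompted for only in the proned arm, which risks overstating them there, and the endpoint is worded only as a decrease although skin damage is a listed risk

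*Protocol*

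**What the plan says.** Protocol Section 7 makes pressure injury a secondary endpoint, worded as "decreased reports of pressure injuries (as identified by BSLMC protocol"). Section 12 lists "Skin breakdown" among the possible risks to participants. Section 13, on benefits, mentions none for the skin.

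Section 9, step 1 gives the only stated charting schedule for this endpoint. It applies "Every calendar day after the patient has been consented and the intervention is occurring", and under it "the nurse assigned to the patient will chart O2 saturation, any presence of hospital acquired pressure injuries, and need to escalate care". The step continues: "This data will be recorded in the electronic medical record, and members of the research team will daily update the REDCap profile with that data".

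For controls, Section 8 says: "The data from the control group will be collected by a retrospective chart analysis after 14 days past their discharge date". It adds: "The same data will be collected for the control group - except for proning duration/compliance as they will not receive this intervention". Section 18 states: "For our patients assigned to the control group, a waiver of consent will be requested".

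Nursing staff know the assignment. Section 8 marks proned patients with a coloured slider at the door, and Section 15 has the research team brief staff on the intervention at the daily huddle.

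**The concern.** There are two separate faults.

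The first is unequal looking. A study instruction to chart pressure injuries every day is triggered by consent and by proning in progress, so it cannot reach controls. The endpoint counts reports, so it depends directly on how hard nurses look and how faithfully they chart. A difference between arms would mix injury with ascertainment.

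The second is wording. The endpoint is stated as a hoped-for decrease, yet the same document names skin damage as something the intervention may cause. An outcome that is also a listed harm should be defined neutrally, so that an increase is as much a result as a decrease.

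The two faults do not cancel. One can distort the count, and the other narrows what the endpoint is said to be about. Whichever way the result fell, it would be hard to interpret.

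**Working it through.** **The text, side by side**

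| Element | Proned arm | Control arm |
|---|---|---|
| Items | Saturation, pressure injury, escalation (Section 9, step 1) | Same items (Section 8) |
| Prompt to look | Each calendar day (Section 9, step 1) | None stated |
| Start | Consent, with proning under way | None stated; consent waived (Section 18) |
| End | Discharge, transfer or 14 days (Section 8, step 5) | No cut-off stated for the chart review |
| Source | Electronic record, copied daily to REDCap | Electronic record, read more than 14 days after discharge (Section 8) |
| Definition of injury | Hospital protocol (Section 7) | Hospital protocol (Section 7) |

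The items, source and definition match. The prompt and the start do not, and no matching end is fixed for controls. The general retrospective review in Section 8, step 6 names length of stay and escalation but not pressure injury, so it does not supply a common schedule.

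**Direction**

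A prompt raises the share of true injuries that reach the record. Given to the proned arm alone, it raises that arm's count and makes proning look worse. The direction of any effect from the differing windows cannot be told from the text.

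**Size (illustration only)**

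The protocol gives no figure for this endpoint, so there is none to reproduce. Its sample size statement in Section 10 concerns time to discharge, and this point does not depend on it. The only input taken from the protocol is 48 patients per arm. True risks and detection shares are assumptions.

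- Expected reports = 48 × true risk × detection share.
- With equal true risk, apparent risk ratio = detection share when proned ÷ detection share in controls.

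With 95% detection under the prompt:

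- control detection 80%: 0.95/0.80 = 1.19
- control detection 60%: 0.95/0.60 = 1.58
- control detection 40%: 0.95/0.40 = 2.375

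If prompting found every injury, control detection of 80% and 60% would give 1/0.80 = 1.25 and 1/0.60 = 1.67.

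At a true risk of 10% in both arms, the proned arm is expected to show 48 × 0.10 × 0.95 = 4.6 reports. Controls would show 3.8, 2.9 or 1.9 at detection of 80%, 60% or 40%. The spurious gap is then 0.7 to 2.6 patients (4.56 − 3.84 to 4.56 − 1.92).

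**How much a comparison of this size can show**

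Assuming a two-sided 5% test with 48 per arm, power to detect a true doubling is 15% (5% against 10%), 28% (10% against 20%) or 42% (15% against 30%). Power of 80% would need 435, 199 or 121 per arm. Counts this small leave little room for an avoidable ascertainment difference of one or two patients.

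**The case against.** The strongest reply is that both arms draw on the same electronic record, the items are declared to be the same, and the hospital's own protocol defines an injury in both. Daily against late copying into REDCap changes when data move, not whether an injury was seen. All of this stands, and it narrows the fault to prompted against routine charting. If routine skin charting on the unit were already daily, the prompt might add little. The protocol does not say how often it is done, so bias is a risk and is not established.

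Three stronger readings are tempting, and the document does not support them.

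- A reader might infer that the ascertainment difference hides harm from proning. It would tend to do the opposite, because heavier looking in the proned arm inflates that arm's count. Only the wording of the endpoint leans away from harm.
- A reader might infer from that wording that a one-directional test is planned. No test or sidedness is stated for this endpoint, and that may sit in an analysis plan that is not shown. The other endpoints in Section 7 are also phrased as hoped-for directions.
- A reader might extend the point to saturation and escalation, which share the same step. Saturation is already documented at least every 4 hours under the unit protocol (Section 8, step 2). Escalation has a stated oxygen threshold and is obtained by chart review (Section 8, step 6). Both are little affected.

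It is also fair to say that the assumed gap amounts to only a few patients and that this is one of several secondary endpoints.

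**Conclusion.** The point holds in limited form. As written, the plan prompts daily charting of pressure injuries in the proned arm only and gives controls no matching schedule or start point. In a study where nurses know the arm, this creates a risk of detection bias that would tend to overstate injuries with proning. Its size is unknown. Ratios of 1.19 to about 2.4 with no true difference follow only from the assumed detection shares.

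Separately, the decrease-only wording in Section 7 sits badly with the risk listed in Section 12. That is a fault of definition, and it does not show that an increase would go unreported.

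The primary endpoint is untouched and no figure in the protocol changes. The matter should still be corrected: the endpoint is also a listed harm, and the repair is cheap.

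**What to change.** - **Same ascertainment.** Take pressure injuries in both arms from the same scheduled routine nursing skin assessment in the electronic record, or apply the same charting schedule to both arms.
- **Same window.** Count from assignment to the same end of follow-up in each arm (discharge, transfer or day 14), and abstract both arms with one form.
- **One-arm findings kept apart.** A common form is not enough on its own, because findings from the study prompt enter the same record. Leave out of the comparison any injury known only through a prompt given to one arm, and report it separately where the record allows.
- **Neutral endpoint.** In Section 7, define the endpoint as new hospital-acquired pressure injury, compared in both directions and also reported as a safety outcome.

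The cost is revised wording in Sections 7, 8 and 9 and one abstraction form. No extra patients are needed. The small downside is that some real injuries found only by the extra prompt drop out of the comparison. If a common charting schedule is chosen instead, the cost is some added charting for controls, which must be squared with the waiver of consent requested for them.
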